10.19.1 Multiple Imputation

Missing ordinal scale data at scheduled time points will be imputed using multiple imputation. Multiple imputation relies on the assumption of data being missing at random (MAR) i.e. the missingness can be explained by the observed data and missing data does not depend on unobserved data after accounting for observed factors. Subjects will only have missing data imputed for post-baseline scheduled visits (Day 2 to Day 29, Day 60).

The following steps will be used to impute the missing data. Prior to the missing data imputation all observed 8-point ordinal scale data will be re-mapped per Table 3 to ensure discharged subjects with supplemental oxygen use are treated as clinically worse than discharged subjects with no oxygen use. This will also ensure information on at home oxygen use is explicitly contained in the ordinal scale score. The value of the adjusted 8-point ordinal scale to use in the analysis for all days following discharge will be assigned as per Section 10.10. On the day of discharge, the following rules will be used to assign a value of the adjusted ordinal scale:

- If a subject has a scheduled visit with an ordinal scale value other than 2, this value will be used in the analysis for the day of discharge.
- If a subject has a missing assessment or a value of 2 is recorded as the scheduled assessment, a subject will be assigned a value of 1 or 2 on the adjusted 8-point ordinal scale on the day of discharge as outlined in Section 10.10.

If a subject has an ordinal scale value of 8 at any visit or the subject has a date of death, records on or following date of death will be handled as follows in the analysis:

- All days following day of death will be set to 8.
- For the day of death, if the subject has a non-missing value on the ordinal scale that is not a value of 8 this will be the value used in the analysis.
- If a subject has a missing value on the day of death the value of 8 will be used.

Subjects who die will be removed from the Imputation in step 2. Only subjects who have not died will have their data imputed. Following the imputation, data for subjects who died will be included in all imputed datasets as observed.

A random seed of 2188 will be used for all imputation in this analysis.

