This step will only be performed if missing data does not follow a monotone missing data pattern. This step assumes data is multivariate normally distributed which will not be the case for ordinal data. However, as the number of non-monotone data is expected to be small, the overall impact of this partial imputation step on the analysis at the time point of interest will be small. Subjects who died will be included in this step. Further it is accepted that values of 1 and 2 may be imputed for non-monotone data prior to the observed date of discharge. No adjustments will be made for this as these values are theoretically possible.

2. Missing 8 point ordinal scale data at time point X will be imputed for subjects who did not die using a logistic regression model with the factors of
 - a. Treatment group
 - b. Actual baseline ordinal scale score
 - c. Region (Pooled)
 - d. Age (will not be included in the CLASS statement in the PROC MI)
 - e. Post-baseline daily values of adjusted 8-point ordinal scale up to time point X

Values will be restricted to a minimum value of 1 and a maximum value of 7, as values of 8 will not be present in the data per the previous rules outlined. It is noted that at a time point only values of the ordinal scale recorded at the time point will be possible imputed values. Imputed values may be inconsistent with other data, for example it is possible that an imputed value will be 3 (Hospitalized, not requiring supplemental oxygen - no longer requires ongoing medical care) even if supplemental oxygen is documented on the concomitant medication page.

The number of imputations will depend on the percentage of missing data to be imputed and will range from a minimum of 20 to a maximum of 50. The number of imputations will increase from the minimum of 20 to the maximum of 50 according to the formula:

$$\text{Number of imputations} = 20 + 1.5 * (m)$$

where m is the proportion of missing data, expressed as a percentage. The smallest integer that is greater than or equal to the number will be used (note this will be based on missing data present following step 1 and will not include subjects who died in the calculation)

By default SAS PROC MI, uses the option "LIKELIHOOD=NOAUGMENT" for the computation of maximum likelihood estimates. If the maximum likelihood parameter estimates do not exist or any warning results from this option, the option "LIKELIHOOD=AUGMENT" will be used to get the maximum likelihood estimates.

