10.19.2 Multiple Imputation as a Sensitivity Analysis for the Primary Endpoint

As a sensitivity analysis for the primary endpoint, all-cause mortality at Day 60, missing data for Day 60 will be imputed using a logistic regression model and the proportions of deaths at Day 60 analyzed per Appendix 2. The steps for this multiple imputation will follow Section 10.19.1 with the following exceptions:

- Deaths in the data will be included in the imputation model.
- For Step 1, imputation of non-monotone data using MCMC, the maximum value allowed will be 8
- At the imputation step only missing data for Day 60 will be imputed using the following model:
 - Treatment group
 - Actual baseline ordinal scale score
 - Region (Pooled)
 - Age
 - Last known post-baseline ordinal scale value (for subjects with complete data collection up to Day 60, this will be the value collected at Day 29 analysis visit)

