10.19.3 Tipping Point Analysis

To assess the robustness of the efficacy analysis, an additional sensitivity analysis using a tipping point will be performed. Tipping point analysis will be performed for the key secondary endpoints of oxygen supplemental free days up to Day 29, proportion of subjects free of respiratory failure at Day 15, and subjects discharged and free of supplemental oxygen usage at Day 15. A series of analyses will be performed with different values of a shift applied until the analysis conclusion of a statistically significant treatment effect no longer holds. The value of δ that changes the conclusions of the analysis from significant to non-significant will represent the tipping point. The results of the tipping point will be summarized showing the treatment difference, 95% CI and p-values for each level of δ . The analysis will not be performed if the primary efficacy analysis for the endpoints results in a non-significant result.

All-Cause Mortality

For the endpoint all-cause mortality, missing data will be imputed using Section 10.19.2. For each imputed dataset generated, a subject with missing data at Day 60 will be assigned as a death/survival based on the value of the adjusted 8-point ordinal scale. Prior to step 3 (performing the logistic regression analysis on the imputed datasets), a shift will be applied to the number of subjects classified as survivors across the imputed datasets. Among the subjects with missing data in the active arm, the number of survivors in this group will be reduced incrementally across each dataset (i.e. changing the subject from survival status to death status), starting at 1 to a maximum value of the number of subjects with missing data (for example if 10 subjects have a missing data at Day 60 in the active arm, each dataset will have the number of responders reduced from 1 up to 10 in the active arm at Day 60) or until it is not possible to reduce the number of survivors any more in an imputed dataset (i.e all subjects at Day 60 with missing data are set to Death status).

For each incrementally shift in the number of responders across missing data in the active arm, step 3 and step 4 will be performed as in Section 10.19.2. If no tipping point is found by just applying a shift to the number of responders in the active arm, the procedure will be repeated with the number of survivors across subjects with missing data at Day 60 in the placebo arm increased.

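### SAP 10.19.1 step 2 fits the imputation model only to subjects who never die, so Day 15 and Day 29 imputations are conditioned on later survival and come out slightly too favourable

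*SAP*

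**What the plan says.** SAP 10.19.1 imputes missing scores on the adjusted 8-point scale under missing at random. Step 2 is the logistic model that fills scores after withdrawal. For that step it states: "Subjects who die will be removed from the Imputation in step 2. Only subjects who have not died will have their data imputed". No time limit is attached, so the exclusion covers anyone who dies up to Day 60. Imputed scores are confined to 1 to 7, "as values of 8 will not be present in the data per the previous rules outlined", and "at a time point only values of the ordinal scale recorded at the time point will be possible imputed values". The predictors are treatment, baseline score, pooled region, age and "Post-baseline daily values of adjusted 8-point ordinal scale up to time point X". Recorded deaths are added back afterwards, with every day after death set to 8.

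The imputed data sets feed the main analysis of three key secondary endpoints: oxygen-free days to Day 29, free of respiratory failure at Day 15, and discharged and oxygen-free at Day 15. They also feed the sensitivity analysis of time to sustained discharge and several other secondary endpoints. Nothing is imputed in the primary mortality analysis (SAP 12.5.2.1) or in the main discharge analysis (SAP 6.1).

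An observed death scores -1 day if before Day 29 (SAP 12.5.3.3) and non-response if before Day 15 (SAP 12.5.3.4 and 12.5.3.5). SAP 12.5.3.1 expects some data to be missing because the subject's condition worsened.

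The mortality sensitivity analysis in SAP 10.19.2 departs from this rule: "Deaths in the data will be included in the imputation model", with "Last known post-baseline ordinal scale value" among the predictors.

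**The concern.** Under missing at random, a withdrawn subject's Day 15 score is borrowed from subjects with the same history up to that point. Subjects who die on Day 40 have such a history and an observed Day 15 score, and they are likely to be among the sicker subjects at Day 15. Removing them because of what happened later leaves a donor set that is too healthy. The purpose of the rule, not to impute data for the dead, does not require this: days after death are already fixed at 8.

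Withdrawn subjects would therefore be credited with somewhat better outcomes than subjects like them actually had, in the main estimate of three endpoints in the testing hierarchy. For oxygen-free days there is a second effect. An observed death counts as -1, whereas a withdrawn subject can be imputed no lower than 0.

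**Working it through.** **Plan figures borrowed.** The plan gives no figure for this rule, so there is none to reproduce. Its sample-size inputs (SAP 8.1) are 150 per arm, withdrawal w = 0.05, and Day 60 mortality q = 0.10 on placebo and 0.025 on C21. They are coherent. ln(0.975)/ln(0.90) = 0.240, the stated hazard ratio. For 15 v 6 deaths, a pooled z-test gives 0.06/sqrt(0.07 x 0.93 x 2/150) = 2.04, p = 0.042. For 15 v 7 deaths, p = 0.076. The stated detection limit holds.

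**Deaths that cannot be represented.** If withdrawn subjects carry their arm's average mortality, n x w x q gives:
- placebo: 150 x 0.05 x 0.10 = 0.75
- C21: 150 x 0.05 x 0.025 = 0.19

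At twice the average risk these become 1.5 and 0.38.

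**Shift in a Day 15 proportion.** Assume every withdrawal precedes Day 15, every death is a Day 15 non-response, and survivors respond with probability ps (assumed range 0.60 to 0.95). The overstatement per arm is w x q x ps.

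| ps | Placebo | C21 | Shift in C21 - placebo | SE of difference | Shift/SE |
|---|---|---|---|---|---|
| 0.60 | 0.300 points | 0.075 | -0.225 | 5.72 | 0.04 |
| 0.95 | 0.475 points | 0.119 | -0.356 | 3.58 | 0.10 |

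For ps = 0.60 the response rates are 0.60 x 0.90 = 0.540 and 0.60 x 0.975 = 0.585, so SE = sqrt((0.540 x 0.460 + 0.585 x 0.415)/150) = 5.72 points. For ps = 0.95 they are 0.855 and 0.926, and the SE is 3.58 points. At 15 v 6 deaths (q = 0.10 and 0.04) the shift is -0.18 to -0.29 points.

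**How much comes from the survivors-only fit.** An illustration for free of respiratory failure with 10% dead by Day 60. Assume 3% dead by Day 15, 5% alive at score 6 or 7, and half of the 7% later deaths in that group. Probability of failure at Day 15:
- all subjects: 0.03 + 0.05 = 0.080
- subjects alive at Day 15: 0.05/0.97 = 0.052
- subjects who never die: (0.05 - 0.035)/0.90 = 0.017

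With 5% missing, the arm is overstated by 0.05 x (0.080 - 0.017) = 0.32 points. Keeping later deaths in the fit recovers 0.05 x (0.052 - 0.017) = about 0.17 of it. The rest reflects deaths before Day 15. Varying the inputs (3 to 7% dead by Day 15, 5 to 8% at score 6 or 7, half or all later deaths in that group) gives 0.3 to 0.5 points per arm. This ignores conditioning on earlier scores.

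**Oxygen-free days.** With survivor mean D = 15 to 22 days (assumed), the mean shift is w x q x (D + 1):
- placebo: 0.05 x 0.10 x 16 = 0.08 to 0.05 x 0.10 x 23 = 0.12 days
- C21: 0.02 to 0.03 days

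The planned analysis is rank-based (Wilcoxon, Hodges-Lehmann), so these figures show the order of size only.

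**Direction.** With equal withdrawal, the arm with more deaths is flattered more, which is placebo at the planning rates. For the shift to favour C21 under this model, C21 withdrawals must exceed 0.10/0.025 = 4 times placebo, or 0.10/0.04 = 2.5 times at 15 v 6 deaths. If withdrawn subjects have similar mortality in both arms, the shift simply favours the arm with more withdrawals.

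**What the sensitivity analyses reach.** For the Day 15 proportions, the tipping point in SAP 10.19.3 can turn every missing C21 subject into a non-responder, which covers death. For oxygen-free days it turns at most the missing days into days on oxygen, so it stops at the observed oxygen-free days, and nothing assigns -1. It is also conditional: "The analysis will not be performed if the primary efficacy analysis for the endpoints results in a non-significant result". The worst-case analysis in SAP 10.19.4 gives missing scores the other arm's rounded average observed score and does not assign death to withdrawn subjects.

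**The case against.** The case for leaving the rule alone is substantial.

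- **It was deliberate.** The SAP change history for version 1.5 records it, and SAP 10.19.2 reverses it where death is the endpoint. That stands. A reader might take SAP 10.19.2 as proof that SAP 10.19.1 is wrong. It is not, because its target is Day 60 death. It shows only that deaths can be kept in such a model.
- **The cap at 7 does nothing extra at Day 15.** This is correct. Scores 7 and 8 are both non-response, so a reader who blames the cap for error in the Day 15 proportions would be mistaken. The cap matters separately only for oxygen-free days.
- **The effect is tiny and conservative.** This largely stands. Formal testing of these endpoints requires a significant mortality result (SAP 12.0), and with fewer deaths on C21 and balanced withdrawal the bias runs against C21. The documents do not support an inference that the rule manufactures benefit for C21.
- **Sensitivity analyses exist, and the protocol's Day 15 and oxygen-free-days estimands reserve imputation for withdrawals that cannot be followed up.** This is partial cover. Known deaths are used, so fewer than 5% may need imputing, although SAP 12.5.3.1 is worded more broadly. Neither sensitivity analysis corrects the main estimate. The gap at -1 is narrow for a subject withdrawn while still on oxygen, who has few observed oxygen-free days anyway.
- **A full vital-status model would be unstable.** With about 19 planned deaths (15 + 3.75), this is a fair reason not to make one the main analysis.

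**Conclusion.** The point holds in a limited form. Selecting the step 2 model on survival to Day 60 is inconsistent with the assumption the SAP states and with the way it scores observed deaths, and no other section corrects the main estimate. At planning rates the Day 15 difference moves by no more than about 0.23 to 0.36 points, or 0.04 to 0.10 SE, against C21. This assumes 5% withdrawal balanced between arms, average mortality among those withdrawn, and survivor response of 0.60 to 0.95. It scales with the withdrawal rate and with the excess risk of those who withdraw, neither of which the plan can know. It does not extend to the primary mortality analysis or to the main discharge analysis. It is worth correcting because the main part of the repair is nearly free, not because it threatens the trial's conclusions.

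**What to change.** 1. In SAP 10.19.1 step 2, fit the model at each time point to all subjects alive at that time point, including those who die later, using their observed scores up to death. Keep the rule that days after death are 8 and are not imputed. In practice, post-death days can be blanked before step 2 and restored to 8 afterwards.
2. Add one sensitivity analysis for the three key secondary endpoints that allows imputed death for withdrawn subjects. Use the SAP 10.19.2 predictors over pooled intervals (for example to Day 15 and to Day 29) and the existing death rules: non-responder, or -1 day if before Day 29. This covers the deaths before the time point that item 1 leaves out.
3. Let the oxygen-free-days tipping point in SAP 10.19.3 extend to -1, and state that floor.

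Cost: SAP wording and a little more code, with no new data. Deaths per interval will be sparse, so the sensitivity model in item 2 may need the AUGMENT option already in the SAP, or fewer factors. The main analysis carries no such burden.

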10.19.2 Multiple Imputation as a Sensitivity Analysis for the Primary Endpoint

As a sensitivity analysis for the primary endpoint, all-cause mortality at Day 60, missing data for Day 60 will be imputed using a logistic regression model and the proportions of deaths at Day 60 analyzed per Appendix 2. The steps for this multiple imputation will follow Section 10.19.1 with the following exceptions:

- Deaths in the data will be included in the imputation model.
- For Step 1, imputation of non-monotone data using MCMC, the maximum value allowed will be 8
- At the imputation step only missing data for Day 60 will be imputed using the following model:
 - Treatment group
 - Actual baseline ordinal scale score
 - Region (Pooled)
 - Age
 - Last known post-baseline ordinal scale value (for subjects with complete data collection up to Day 60, this will be the value collected at Day 29 analysis visit)

10.19.3 Tipping Point Analysis

To assess the robustness of the efficacy analysis, an additional sensitivity analysis using a tipping point will be performed. Tipping point analysis will be performed for the key secondary endpoints of oxygen supplemental free days up to Day 29, proportion of subjects free of respiratory failure at Day 15, and subjects discharged and free of supplemental oxygen usage at Day 15. A series of analyses will be performed with different values of a shift applied until the analysis conclusion of a statistically significant treatment effect no longer holds. The value of δ that changes the conclusions of the analysis from significant to non-significant will represent the tipping point. The results of the tipping point will be summarized showing the treatment difference, 95% CI and p-values for each level of δ . The analysis will not be performed if the primary efficacy analysis for the endpoints results in a non-significant result.

All-Cause Mortality

For the endpoint all-cause mortality, missing data will be imputed using Section 10.19.2. For each imputed dataset generated, a subject with missing data at Day 60 will be assigned as a death/survival based on the value of the adjusted 8-point ordinal scale. Prior to step 3 (performing the logistic regression analysis on the imputed datasets), a shift will be applied to the number of subjects classified as survivors across the imputed datasets. Among the subjects with missing data in the active arm, the number of survivors in this group will be reduced incrementally across each dataset (i.e. changing the subject from survival status to death status), starting at 1 to a maximum value of the number of subjects with missing data (for example if 10 subjects have a missing data at Day 60 in the active arm, each dataset will have the number of responders reduced from 1 up to 10 in the active arm at Day 60) or until it is not possible to reduce the number of survivors any more in an imputed dataset (i.e all subjects at Day 60 with missing data are set to Death status).

For each incrementally shift in the number of responders across missing data in the active arm, step 3 and step 4 will be performed as in Section 10.19.2. If no tipping point is found by just applying a shift to the number of responders in the active arm, the procedure will be repeated with the number of survivors across subjects with missing data at Day 60 in the placebo arm increased.

The choice of the subject to change from a survivor to death will be done at random. Using the random seed of 150822, each subject with missing data will be assigned a numeric value. The subject's values will be changed incrementally based on the numeric order generated by this process.

Respiratory Failure Free at Day 15/ Discharged and Free of Supplemental Oxygen Usage at Day 15

For these endpoints, a similar approach as all-cause mortality will be applied. For each imputed dataset as generated per Section 10.19.1 a subject will be assigned as a responder/non-responder depending on the value of the adjusted ordinal scale. For each imputed dataset, a shift will be applied to the number of responders across the imputed datasets. Among the subjects with missing data in the active arm, the number of responders in this group will be reduced incrementally across each dataset, starting at 1 to a maximum value of the number of subjects with missing data at Day 15 or until it is not possible to reduce the number of responders any more in an imputed dataset (i.e all subjects at Day 15 with missing data are set to be non-responder). If a shift is not found by just applying to the active arm, a shift will be applied to the Placebo arm (increasing the number of responders). The choice of which subject to change from responder to non-responder will be assigned following the approach for all-cause mortality.

Number of Supplemental Free Days up to Day 29

For the endpoint oxygen supplemental free days up to Day 29, the imputation as described in Section 10.19.1 will be performed and for each imputed dataset the number of days oxygen free will be tabulated. Then for subjects in the active arm with missing data up to Day 29, the number of days oxygen free will be reduced incrementally starting at 1 up to the number of days the subject had a missing value. For each reduction, the analysis as described in step 3 and step 4 in Section 10.19.1 will be performed. If no tipping point is found by just applying a shift to the number of days in the active arm, the procedure will be repeated with the number of days across subjects with missing data in the placebo arm increased.

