10.13 Number of Oxygen Free Days

Subjects will be considered oxygen free on a trial day if they do not have supplemental oxygen usage on that day. Supplemental oxygen usage is defined in Section 10.10 and subjects will be assessed for supplemental oxygen usage on each post treatment day up to trial Day 29 (i.e. from trial Day 2 to Day 29).

The number of oxygen free days for a subject will be the sum of the number of oxygen free days in hospital and number of oxygen free days at home if applicable. These days do not need to be consecutive. Missing data will be imputed as per Section 10.19.1.

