3. Imputed values from each of the imputed datasets in step 2, data for subjects who died and non-missing data will be used to calculate the responder status for a subject at a time point for the following endpoints:

Sensitivity Analysis for Time to Sustained Hospital Discharge

For each of the imputed datasets, the time to sustained hospital discharge will be derived. If a subject has an observed or imputed score of ≤ 2 on the ordinal scale where for all subsequent visits the observed or imputed score stays at or below 2 the earliest occurrence will be considered the time to sustained hospital discharge. Note for subjects with no missing data, the time to sustained discharge will be per the rules in Section 10.12. If a subject was re-hospitalized for a non-COVID-19 related reason, the subject will not be considered discharged during this re-hospitalization period for this analysis. For all subjects who do not have the event or who die, they will be censored at Day 60. The calculation will be as follows:

$$\text{Time to sustained discharge (Days)} = \text{Date of Event or Censor} - \text{Date of first dose of IMP} + 1$$

For subjects where the event occurs on an imputed visit, the value of time to sustained discharge will be set to the trial day of the imputed visit (i.e. if the event first occurs for Day 29 and is an imputed value, the time to sustained discharge will be set to 29). For each of the datasets the analysis (stratified log-rank) as per Section 12.5.3.2 will be implemented.

Number of Days Oxygen Free

A subject will be considered as oxygen free at a time point if the observed and imputed value of the adjusted 8-point ordinal scale is 1, 3 or 4. For each of the datasets imputed in step 2, the analysis as per Section 12.5.3.3 will be implemented.

Proportion of subjects free of respiratory failure at Day 8, 15, 22, 29, 60

A subject will be considered a responder at a time point if the value of the 8-point ordinal scale is ≤ 5 . For each of the datasets imputed in step 2, the analysis as per Section 12.5.3.4 will be implemented.

Subjects discharged and free of supplemental oxygen at Day 8, 15, 22 and 29

A subject will be considered a responder at a time point if the value of the adjusted 8-point ordinal scale, observed and imputed, is 1. For each of the datasets imputed in step 2, the analysis as specified in Section 12.5.3.5 will be implemented.

Number of Days Free of Respiratory failure

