12.5.3.2 Time to Sustained Hospital Discharge

Time to sustained hospital discharge, will be defined as time to discharge after which no re-hospitalizations due to COVID-19 occur. Please refer to Section 10.12 for further details on this calculation.

Treatment groups will be compared using a stratified log-rank test adjusting for treatment, actual baseline disease severity and region. The size of the treatment effect will be estimated as a hazard ratio, obtained using a Cox proportional hazards regression model and the Cox regression model will include a factor for

randomized treatment, baseline disease severity and region. The estimated hazard ratios for each treatment group will be presented together with the corresponding 95% CI (based on Wald test).

Analysis will be illustrated using a Kaplan-Meier plot and the median time to hospital discharge will be estimated with 95% CIs for each treatment group. Subjects who die prior to Day 60 will be censored at Day 60 and trial withdrawals prior to Day 60 due to other causes than death without fulfilling the event will be censored at day of withdrawal. Subjects still in trial but not discharged from hospital at Day 60 will be censored at their Day 60 trial visit.

12.5.3.3 Oxygen Supplemental Free Days up to Day 29

Oxygen supplemental free days up to Day 29 will be defined as the number days for each subject with a score of ≤ 4 and no use of COVID-19 related supplemental oxygen. Refer to Section 10.13 for the derivation of number of oxygen free days.

Subjects who die prior to Day 29 will be given a value of -1 days in the analysis. Subjects who withdraw from the trial prior to Day 29 and have missing data will have their data multiply imputed as per Section 10.19.1. Subjects who chronically used supplemental oxygen prior to their COVID-19 illness will be considered oxygen free when they return to the same level of oxygen support they had been using prior to COVID-19.

Treatment groups will be compared using the Wilcoxon rank-sum test (using p-values) and the treatment difference will be expressed as the Hodges-Lehmann difference in median number of days with 95% CIs. All collected data post treatment will be used. Summary statistics for the number of oxygen free days will also be presented for each treatment group. A cumulative distribution plot of the number of oxygen free days by treatment arm will also be produced.

12.5.3.4 Subjects Free of Respiratory Failure at Day 15

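### The tipping-point shift for oxygen-free days has no floor, so some living withdrawn subjects can score below the -1 given to deaths

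*SAP*

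**What the plan says.** SAP 10.19.3 describes a tipping-point analysis for the third-ranked endpoint in the testing hierarchy, supplemental oxygen-free days up to Day 29. After multiple imputation, "for each imputed dataset the number of days oxygen free will be tabulated". In the active arm, the total of each subject with missing data "will be reduced incrementally starting at 1 up to the number of days the subject had a missing value". If no tipping point is found, "the procedure will be repeated with the number of days across subjects with missing data in the placebo arm increased".

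Four other provisions bear on this:

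- SAP 10.13 sets the counting window, "i.e. from trial Day 2 to Day 29", which is 28 days.
- SAP 10.19.1 counts a day as oxygen free if "the observed and imputed value of the adjusted 8-point ordinal scale is 1, 3 or 4". Imputed scores may be anything from 1 to 7, so a missing day can be imputed as a day on oxygen.
- SAP 12.5.3.3 states: "Subjects who die prior to Day 29 will be given a value of -1 days in the analysis". The comparison is a Wilcoxon rank-sum test.
- SAP 10.19 makes death the worst outcome in every efficacy analysis.

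For the two Day 15 endpoints, the same section ends the shift at the number of subjects with missing data "or until it is not possible to reduce the number of responders any more in an imputed dataset". The mortality paragraph has an equivalent stop. The oxygen-free-days paragraph has none.

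**The concern.** The limit is placed on the size of the shift, not on the value that results. It would act as a floor only if every missing day had been imputed oxygen free. Otherwise the rule subtracts days that were never counted. It first eats into days the subject was actually observed to be oxygen free, and then goes below zero.

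Once a living subject passes -1, the order against every death is reversed, contrary to SAP 10.19. SAP 10.19.3 requires the treatment difference, confidence interval and p-value to be shown at each shift, so results based on impossible counts would be reported. A tipping point reached only through such counts says nothing about robustness to plausible missing data.

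**Working it through.** **Notation.** For one subject, o is observed oxygen-free days, m is missing days (29 minus the last observed day), k is missing days imputed oxygen free (0 to m), and δ is the shift, at most m.

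**Active arm.** The shifted value is o + k - δ. At δ = m it is o - (m - k), that is, observed oxygen-free days minus imputed on-oxygen days. The lowest value a subject could truly have is o. Hence at the full shift:

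- the value is below the observed count whenever k < m;
- it is negative when m - k > o;
- it is below the death score when m - k > o + 1.

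| Last observed day | o | m | k | Total | Value at δ = m | Lowest possible | Below -1 from δ = |
|---|---|---|---|---|---|---|---|
| 5 | 0 | 24 | 10 | 10 | -14 | 0 | 12 |
| 5 | 0 | 24 | 15 | 15 | -9 | 0 | 17 |
| 10 | 4 | 19 | 10 | 14 | -5 | 4 | 16 |
| 14 | 0 | 15 | 5 | 5 | -10 | 0 | 7 |
| 10 | 4 | 19 | 19 | 23 | 4 | 4 | never |

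The last row is the harmless case: every missing day was imputed oxygen free.

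Enumerating every combination of last observed day (1 to 28), o and k gives 4,466 cases. Of these, 2,135 end negative: 1,925 below -1 and 210 tied with death at -1. This is an unweighted count, not a probability.

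**Placebo arm.** Suppose the repeated procedure keeps the missing-day limit. A subject with last observed Day 5, o = 0 and k = 15 then reaches 15 + 24 = 39 days. The most that subject could have is o + m = 24, and nobody can exceed 28.

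**Size.** The plan gives no figure to reproduce, and the effect depends on recovery, death and withdrawal patterns that the documents do not supply. The figures below are illustrative simulations on assumed patterns, with 150 per arm in the first two.

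- *8 of 150 C21 subjects withdrawn, close to the 5% in SAP 8.1.* Assumed: exponential time on oxygen with mean 9 days on placebo and a recovery rate 1.4 times higher on C21; deaths 8% and 4%; last observed day spread over Days 3 to 21. Of 1,000 trials, 806 were significant. About 17% of withdrawn subjects ended below -1, and about 80% of significant trials had at least one such subject. Whether, or at which δ, significance was lost differed between the unfloored and floored rules in 3.8%. The share tipping at all was 29.9% without the floor and 29.3% with it.
- *5% withdrawn, varying the share withdrawn while in hospital.* Assumed Day 29 deaths were 2.5% and 8%. Where 73 to 83% of trials were significant, the share tipping only for want of a floor was 0 to 0.4% with none in hospital, 1 to 2% with one third, 4% with two thirds and 6 to 7% with all. Where 98% of trials were significant, the four figures were 0, 1.0, 1.3 and 1.8%.
- *7% withdrawn, all in hospital.* One run gave 8%. Another, with 1,030 significant trials of 1,500, gave 54.7% tipping without the floor and 45.8% with it, a difference of 8.9 points. In that run 58% of withdrawn subjects ended below -1.

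**The case against.** The strongest reply is that this barely matters. SAP 12.5.3.1 lists discharged subjects who do not return first among the expected causes of missing data. If their missing days are imputed oxygen free, they never fall below their observed count. The rank test also limits the damage. With 8 withdrawn subjects and 15 placebo deaths (the planning figure to Day 60), dropping past every death moves the rank-sum statistic U by at most 8 × 15 = 120. Its standard deviation is √(150 × 150 × 301 / 12) ≈ 751, so z moves by about 0.16. Passing placebo zeros, and falling from an observed count above 0, adds somewhat to this. Only borderline results can change, and reporting every δ makes a tip at an extreme shift visible. The missing stop also looks like an omitted clause that programming might catch.

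Most of this stands and sets the severity. It does not rescue the text, which subtracts from the tabulated total rather than turning imputed oxygen-free days into days on oxygen. SAP 12.5.3.1 also expects withdrawals through clinical worsening, which are the vulnerable cases. The value of 0 in SAP 10.19.4 belongs to the worst-case analysis and supplies no floor here.

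Three stronger readings are tempting but unsupported. A reader might infer that withdrawn subjects in general end below deaths; only those with m - k > o + 1 do. A reader might infer that the placebo shift is unlimited; repeating the procedure most naturally carries over the missing-day limit, although totals can still exceed 28. A reader might infer that a robust result would commonly be reported as fragile; the highest figures come from withdrawal above the SAP's 5% and entirely in hospital.

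**Conclusion.** Wrong as written; minor. As an active-arm rule it yields impossible values and, for some living subjects, scores below death, against SAP 10.19. The arithmetic follows from the text alone. The practical size does not: roughly 0 to 9% of significant trials have a changed tipping result, and about 4% with 8 of 150 withdrawn. The 4% also counts trials where only the tipping δ moved; most of the other figures count trials that tip solely for want of a floor. No separate size was estimated for the placebo part.

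The main analysis is untouched. The tipping-point analysis runs only if this endpoint is significant, which is a formal conclusion only if mortality and time to sustained discharge have also succeeded. The active-arm defect works against C21, and so does the placebo one, so neither can inflate a claim of efficacy.

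**What to change.** Amend the oxygen-free-days paragraph of SAP 10.19.3 as follows:

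- **Active arm:** cap each subject's reduction at the missing days imputed oxygen free in that dataset. The count is then floored at observed oxygen-free days and never falls below 0.
- **Placebo arm:** cap each increase at the missing days imputed as on oxygen. The count then never exceeds observed oxygen-free days plus missing days, and never 28.
- **Stop** when no subject can be shifted further, as the mortality and Day 15 paragraphs already do.

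With these caps the first and third table rows end at 0 and 4 instead of -14 and -5. The cost is a sentence or two in the SAP and a line of code per arm, with no change to data collection or to the main analysis.
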